Study Protocol and Statistical Analysis Plan

Protocol Title: Depression Care to Improve Adherence to PMTCT Care Continuum and Pregnancy Outcomes

NCT03892915

Date: 4/16/19

Investigators:

1. [name], Makerere University, School of Public Health (Co-PI)
2. [name]; RAND Corporation (Co-PI)
3. [name]; Ministry of Health (Co-I)
4. [name], Makerere University, School of Medicine (Co-I)
5. [name]; Mulago Hospital (Co-I)
6. [name]; Mildmay Uganda (Co-I)

Brief outline of the rationale for the study

Depression is common among HIV+ pregnant women, in both prenatal and post natal phases and depression often impedes adherence to PMTCT care, parenting, and early child health development. Treating depression could mitigate these consequences and help ensure optimum pregnancy and maternal and child health outcomes. The proposed cluster randomized controlled trial will compare the effects of evidence-based depression care vs. usual care on adherence to each step of the PMTCT care continuum at 8 ANC clinics and with 400 HIV+ depressed pregnant women (50 per site). Four (4) clinics will implement usual care and 4 will implement usual care plus depression care [anti depressant therapy(ADT) and problem solving therapy (PST)]. Peer mothers will be trained to assist in depression screening and implement PST, while nurses will be trained to diagnose depression and provide ADT, under the supervision of psychiatric specialists. PST will be recommended for all women deemed eligible for treatment, while ADT will be recommended for only those with severe or refractory depression.

Primary aims of the study:

1. Integrate evidence-based PST and ADT into usual care, using the gold standard, stepped care approach.
2. Assess whether the integrated depression care model is superior to usual care on (1) adherence to each step of the PMTCT care continuum and maternal viral suppression (primary outcomes); (2) prevention of infant HIV infection, and maternal and child health outcomes (secondary outcomes), and 3) depression treatment uptake and depression alleviation (depression care processes).

Secondary aim;

Examine how (1) depression and (2) depression alleviation are associated with maternal viral load, adherence to each step of the PMTCT care continuum, and mother and child health outcomes; and identify potential mediators (e.g., HIV disclosure; stigma; problem solving skills) of these relationships.

Methods

The two arm cluster RCT will compare the effects of task-shifted, evidence-based depression care vs. usual care on adherence to each step of the PMTCT care cascade at 8 ANC clinics in Uganda. At 4 experimental sites, task-shifted, depression care will include (1) depression screening and psychoeducation, (2) depression diagnosis, and (3) provision of evidence-based problem solving therapy (PST), or antidepressant therapy (ADT) for those with severe and refractory depression (or who decline PST), to be implemented by trained peer mothers and midwife nurses. The 4 control sites will use usual care services for managing depression, which consist of the FSG program and referrals to a mental health specialist. At each site, 50 HIV+ newly pregnant women (total n=400) who screen positive for potential depression will be enrolled and followed until 18-months post-delivery to assess how depression and depression alleviation relate to primary (adherence to each component of the PMTCT care continuum, maternal virologic suppression) and secondary (infant HIV status; post-natal maternal and child health outcomes) outcomes, as well as processes of depression care (treatment uptake and depression alleviation among clinically depressed patients). The PST/ADT treatment will be provided only to study participants, not all depressed clients, because our focus is the effects of depression treatment on PMTCT adherence and pregnancy outcomes, not implementation research for scaling

up the model in ANC care (with HIV and non-HIV women), which is a much broader focus. A cost-effectiveness analysis will be used to compare the two study arms.

We will enroll all consenting eligible clients and survey them at baseline, month 6, 12 and 18 following delivery. For those who miscarry, a final survey will take place 6 months after the miscarriage to assess successful transition to receive HIV care at the HIV clinic. At all sites, HIV+ adult patients who are early enough in their gestation period to be eligible for the study will be informed of the study and screened for potential depression by trained peer mothers using the EPDS-2. The screening will take place in a private room and those who screen positive will receive depression psycho-education. Eligible women who express interest in participating in the study will be connected by the peer mother to the study coordinator (via phone if the coordinator is not at the clinic that day) so that the coordinator can describe the study in detail, confirm eligibility and obtain written consent; these procedures are done during the same clinic visit, or the next day that the coordinator is at the clinic.

Qualitative data will be collected from peer mothers and midwife nurses at baseline, 12 and 24 months, at the intervention sites to assess: successes and challenges in screening, diagnosing and treating patients for depression; the training and supervision process; and impact of depression and its treatment on pregnancy and PMTCT care, clinic functioning, and provider job satisfaction and burnout. We will also interview 40 client participants (20 clinically depressed who were treated, and 20 not treated) at their final study assessment to assess their experiences with pregnancy.

Data analysis

Statistical Analysis. We will first compare clinic-level differences, using standard t-tests or, where the observations per clinic vary, t-tests weighted by cluster-size. Like most cluster RCTs, we do not have the 20+ clusters needed to reliably adjust standard errors for clustering, so we will use the conventional approach of using regression methods on individual level data for most analyses, but will conduct sensitivity analyses using a range of plausible ICC values for the outcomes.

Primary Aim 1: intervention effects on primary outcomes. We will use logistic regression to test for differences between the two study arms on (i) PMTCT adherence, coded as a binary variable, at each stage of the PMTCT care continuum, and (ii) maternal viral suppression. The regression models will include patient characteristics such as age, CD4 and HIV disclosure status that may explain variance in observed differences. We will also explore significant interactions between the covariates and study arm to assess which patient types are likely to be adherent and virally suppressed in depression care vs. usual care. The effect of depression care on PMTCT adherence will be examined using intention to treat as the primary approach. We will use a repeated-measures model that will allow us to incorporate correlation in measurements of each person over time. The sample size of individuals for such models is adequate. The model formulation is: $\text{adherence}_{it} = \alpha + \beta G_i + \gamma(t) + \delta G_i \times t + \theta_i + \varepsilon_{it}$ where i is individual, t is continuous time, G is binary indicator of treatment group, β allows for baseline differences between the two groups, γ is the time trend in the outcome common to both groups, and δ is the interaction of treatment group and time, and shows the intervention effect (i.e. effect of depression care relative to usual care). Further, θ_i is an individual-level random effect (to allow for variation across participants) and ε_{it} is time period-specific error. With a vector of individual-level covariates X_i included in the model, we can assess main effects of patient characteristics and interactions between these X_i and indicator of treatment group. Such a model will allow us to test for significance of potential mediators: e.g., do effects of the depression care model vary by the patient's physical health at baseline? As the primary approach is intention-to-treat, the estimates will capture the average benefit for depressed patients, regardless of compliance or use of depression treatment. A secondary "completers only" analysis will be conducted as well. In addition, we will conduct a dose-response type analysis to explore the relationship between continuous implementation variables (e.g. treatment sessions attended), which are collected for all participants, and primary outcomes. Further, to better understand how or why the intervention exerted its effect, we will model the relationship

between fidelity measures (e.g. quality) and primary outcomes, as well as conduct mediation analysis including fidelity as a mediator, in the subgroup of patients enrolled in clinics receiving the intervention arm (depression care).

Secondary Aims 1 & 2: Explore relationship of depression and depression alleviation with primary and secondary outcomes. *Hypothesis: Depression will be associated with lower adherence to each step of the PMTCT care continuum, maternal viral suppression and maternal and child health, while depression alleviation will be associated with better adherence, viral suppression and health outcomes.* We will conduct (unadjusted) bivariate analysis to initially examine significant associations between baseline depression ($EPDS \geq 13$) and depression alleviation over time with the primary and secondary outcome measures. Next, longitudinal analysis will be conducted to incorporate repeated observations of individuals and to explore the relationship between change in depression and outcomes over time, and to test whether depression alleviation ($EPDS \leq 6$) is related to change in these outcomes. Models will control for observed individual characteristics and unobservables through a random effect term to incorporate characteristics that may affect both depression and the dependent variables. However, this model does not control for simultaneity (e.g., change in viral suppression leads to lower depression). With multiple time-points, instrumental variable approaches combined with fixed effects potentially can deal with this problem, using baseline depression to predict change in depression from time 2 to time 3, if baseline depression is strongly correlated with change in depression over time. The fixed effects model will indicate important time trends in depression and the primary and secondary outcomes.

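### Several co-primary outcomes have no stated success rule, and for adherence the plan does not say whether the per-stage arm difference or the arm-by-time term decides

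*Combined protocol and SAP*

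**What the plan says.** Primary aims of the study sets one superiority question over "adherence to each step of the PMTCT care continuum and maternal viral suppression (primary outcomes". Methods repeats the set, as "primary (adherence to each component of the PMTCT care continuum, maternal virologic suppression", with no order among its members. Neither section lists or counts the steps. Methods says the investigators will enrol women and "survey them at baseline, month 6, 12 and 18 following delivery", but does not link those times to particular steps or to viral suppression.

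The section Primary Aim 1: intervention effects on primary outcomes first applies logistic regression to arm differences on "PMTCT adherence, coded as a binary variable, at each stage of the PMTCT care continuum, and (ii) maternal viral suppression". For adherence it then adds: "We will use a repeated-measures model that will allow us to incorporate correlation in measurements of each person over time". In that model the coefficient of treatment group, β, is described as a baseline difference between groups. The coefficient δ is "the interaction of treatment group and time, and shows the intervention effect". Intention to treat is named as the main approach, which settles who is analysed but not which test decides.

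No section gives a significance level, a sidedness, a multiplicity method, or a statement of whether superiority is claimed outcome by outcome, only if all succeed, or on any one success.

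**The concern.** Two things are left open that should be fixed before the data are seen.

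The first is the success rule. If each outcome carries its own claim, each test keeps its own error rate and no overall claim follows. If all must succeed, no adjustment is needed but power falls. If one success is enough, the false-positive rate exceeds the nominal level. The text allows all three.

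The second is the deciding effect for adherence. The per-stage logistic comparison asks whether the arms differ at a step. The interaction asks whether the gap between arms changes linearly with time. A lasting benefit that is already present at the first post-delivery visit answers yes to the first question and can answer no to the second. If both analyses are run and neither is named as decisive, the reported conclusion can follow whichever result is more favourable.

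**Working it through.** **No figure to reproduce.** The plan states no significance level, power or error rate, so the checks below are new.

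**1. Do the two adherence effects measure the same thing?**

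Inputs: visits at months 6, 12 and 18 after delivery, and the linear model with δ on group × time, both from the plan. The benefit patterns are illustrations. Time from baseline to delivery is not given, so baseline is assumed to lie 3 to 7 months before delivery, with no difference between arms.

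With complete data, the estimate of δ is the least-squares slope of the arm difference d(t) on time: δ = Σ(t − t̄)d(t) / Σ(t − t̄)².

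*Visits 6, 12, 18 only.* t̄ = 12, deviations −6, 0, 6, sum of squares 72.
- Constant 10, 10, 10: (−60 + 0 + 60)/72 = 0. The whole benefit goes into β, the term the plan describes as a baseline difference.
- Waning 15, 10, 5: (−90 + 0 + 30)/72 = −0.83 points per month.

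*Baseline at −3 months, difference 0.* t̄ = 8.25, deviations −11.25, −2.25, 3.75, 9.75, sum of squares 240.75.
- Constant: 10 × (−2.25 + 3.75 + 9.75)/240.75 = 112.5/240.75 = 0.47.
- Waning: (−33.75 + 37.5 + 48.75)/240.75 = 52.5/240.75 = 0.22.

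*Baseline at −7 months, difference 0.* t̄ = 7.25, deviations −14.25, −1.25, 4.75, 10.75, sum of squares 342.75.
- Constant: 142.5/342.75 = 0.42.
- Waning: (−18.75 + 47.5 + 53.75)/342.75 = 82.5/342.75 = 0.24.

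| Arm difference at 6, 12, 18 | Mean difference | δ, post-delivery visits only | δ, with zero baseline difference |
|---|---|---|---|
| 10, 10, 10 | 10 | 0 | 0.42 to 0.47 |
| 15, 10, 5 | 10 | −0.83 | 0.22 to 0.24 |

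The same average benefit gives interactions that differ in size, and in sign when baseline is left out. A step observed only once has no time dimension and cannot support δ at all.

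**2. What would an any-one-success rule cost in error?**

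Assumptions: valid two-sided 5% tests and true null effects on every outcome. The smallest number of primary outcomes that the wording allows is k = 3 (at least two steps, plus viral suppression).
- Independent tests: 1 − 0.95³ = 14.3%.
- Equally correlated normal test statistics, critical value 1.96, by numerical integration over a shared factor: 12.5% at correlation 0.5 and 8.4% at correlation 0.9.

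Steps observed in the same women are probably positively correlated, so 14.3% is an upper end for k = 3.

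**The case against.** A reader might infer that the trial's false-positive rate is inflated as planned. The documents do not support that. Asking about superiority on each step, and testing at each stage, reads most naturally as outcome by outcome, and no sentence makes a global claim on any one success. Under a per-outcome or all-must-succeed rule there is no such inflation. This objection stands, and the error rates above hold only for one reading, which is neither stated nor excluded.

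A reader might also infer that the interaction would miss a real, constant benefit altogether. That holds only if the model is fitted to the post-delivery visits alone. Baseline is a planned survey and the model has a baseline term. With a zero baseline difference included, both effects favour depression care in both examples. What remains is that they are still different quantities, and that a step which cannot be measured at baseline would leave only the later visits.

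Nor are there two effects both labelled as the intervention effect: only δ is called that, and the logistic models are said to test differences. The repeated-measures model follows directly on the intention-to-treat statement, so it could be meant as the main adherence model, or the two models could serve different steps. Either is possible. The plan says neither, so the gap is in how the models relate.

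Finally, the sentence "We will first compare clinic-level differences, using standard t-tests" might be taken as a third competing test. The plan puts it first and then says it will "use the conventional approach of using regression methods on individual level data for most analyses", which suggests a preliminary comparison. It does not add to this point.

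**Conclusion.** The point holds in a limited form. The plan has several primary outcomes under one superiority aim with no success rule. For adherence it gives a per-stage arm difference and an arm-by-time term without saying which decides.

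The stronger part is the deciding effect, because the term the plan says shows the intervention effect does not answer the aim: it can be 0 or negative over the post-delivery visits when the average benefit is 10 points. That rests on the model's linear scale and on the illustrative patterns, and the with-baseline values rest on the assumed 3 to 7 months.

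The missing success rule is an omission whose consequence depends on the reading. Its size, 8.4% to 14.3% against 5% for k = 3, applies only if any one success counts, with valid 5% tests. This should be corrected before analysis; confidence is medium, because the harm depends on choices that the plan leaves open.

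**What to change.** Before analysis, in the SAP:

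1. List the continuum steps, with an assessment time for each and for viral suppression.
2. Make the between-arm difference at each step the decisive adherence effect, since that is what the primary aim asks. Label the arm-by-time term supportive.
3. State whether superiority is claimed per outcome, only if all succeed, or on any one success. If any one success counts, control family-wise error across the primary outcomes by Holm's procedure or by a fixed sequence that the sponsor orders.

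**Cost.** Items 1 and 2 need wording only and no new data. Item 3 costs power only if the rule is stricter than per outcome. With Holm and large-sample tests, take an outcome with 80% power at 1.96, so an expected test statistic of 1.96 + 0.84 = 2.80. The first-step critical value is 2.39 for k = 3, and power there is Φ(2.80 − 2.39) = 66%. For an assumed k = 5 it is 2.58 and 59%; for an assumed k = 9 it is 2.77 and 51%. An all-must-succeed rule with 80% power per outcome and k = 3 succeeds with probability 0.8³ = 51% if the tests are independent, and 61% at correlation 0.5. A fixed sequence keeps 80% for its first outcome only.

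Whether the decisive test must respect randomisation by clinic is a separate issue with its own cost. It is not included in these figures and should be raised separately.

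### The logistic tests of the primary outcomes ignore the 8 randomised clinics and the valid clinic-level test is not made decisive; type I error is about 11-29%, not 5%, if the ICC is 0.01-0.05

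*Combined protocol and SAP*

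**What the plan says.** The outline and Methods describe a two-arm cluster randomised trial with 8 antenatal clinics, 4 per arm, and 50 women per clinic (400 in all). The primary outcomes are adherence at each PMTCT step and maternal viral suppression, and the question is one of superiority.

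The Statistical Analysis paragraph under Data analysis makes three statements about clustering:

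- It starts with clinic summaries: "We will first compare clinic-level differences, using standard t-tests", weighted by cluster size where clinic numbers vary.
- It then says that "we do not have the 20+ clusters needed to reliably adjust standard errors for clustering".
- For that reason it turns to "regression methods on individual level data for most analyses, but will conduct sensitivity analyses using a range of plausible ICC values for the outcomes".

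The Primary Aim 1 paragraph names the test of the primary outcomes: "We will use logistic regression to test for differences between the two study arms". The covariates named are patient characteristics (age, CD4, disclosure). No clinic term, cluster-robust variance or small-sample correction appears.

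The same paragraph gives a repeated-measures model whose only random effect is for the individual woman. Its coefficient delta "is the interaction of treatment group and time, and shows the intervention effect". On size, the paragraph says: "The sample size of individuals for such models is adequate".

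**The concern.** Women at one clinic share staff, stock, catchment and local practice, so their outcomes are likely to be correlated. With only 4 clinics per arm, chance differences between clinics do not average out. A logistic regression that treats 400 women as independent can read those differences as an effect of depression care, and its intervals are too narrow.

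The reason offered does not support the choice. Having fewer than 20 clusters is an argument against large-sample robust standard errors. It is not an argument for leaving clustering out, because a t-test on 8 clinic summaries is valid at this size and the plan already mentions one.

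The plan does not say which result supports a superiority claim. The clinic-level tests are not tied to the primary outcomes, the ICC values are left open, and nothing says what happens if the clinic-level and individual-level results differ.

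**Working it through.** **Inputs.** From the documents: 8 clinics, 4 v 4, m = 50 women per clinic, 8 × 50 = 400. There is no alpha, power, effect size, ICC or design effect, so there is no power calculation to reproduce. Assumed: two-sided 5% level; ICC from 0.001 to 0.05.

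**1. Logistic test without clinic.** Design effect DE = 1 + (m − 1) × ICC. Actual type I error = 2 × [1 − Φ(1.96/√DE)]. Intervals are too narrow by a factor of √DE.

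| ICC | DE (m = 50) | √DE | Effective N (400/DE) | Type I error |
|---|---|---|---|---|
| 0.001 | 1.049 | 1.02 | 381 | 5.6% |
| 0.005 | 1.245 | 1.12 | 321 | 7.9% |
| 0.01 | 1.49 | 1.22 | 268 | 10.8% |
| 0.02 | 1.98 | 1.41 | 202 | 16.4% |
| 0.05 | 3.45 | 1.86 | 116 | 29.1% |

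If 35 women per clinic remain, DE = 1 + 34 × ICC, which gives 1.34 and 9.0% at ICC 0.01, and 2.70 and 23.3% at ICC 0.05.

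**2. Check by simulation.** Beta-binomial outcomes, 8 clinics of 50, no true effect, 200,000 trials per setting, true rates 0.50, 0.70 and 0.85:

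- The logistic Wald test rejected in 10.6-11.1% of trials at ICC 0.01, 16.1-16.5% at 0.02 and 29.0-29.4% at 0.05.
- The unweighted clinic-level t-test (8 − 2 = 6 df) rejected in 4.9-5.1% at every ICC from 0 to 0.05.

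At a rate of 0.70, about 65% (ICC 0.01) and 83% (ICC 0.05) of the false-positive logistic results were not significant at clinic level. The unaddressed conflict would therefore be common.

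**3. Patient covariates do not repair it.** With one patient covariate and clinic SDs of 0.21 and 0.49 on the logit scale (ICC about 0.008 and 0.043; 4,000 trials), the adjusted logistic test without clinic rejected in 10.0% and 27.8%. A t-test on covariate-adjusted clinic residuals, 6 df, rejected in 4.9% and 5.0%.

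**4. Repeated-measures effect (delta).** In the linear form the plan writes, a clinic effect that is constant over time shifts every visit equally and cancels from the slope difference. Delta is inflated only by clinic-by-time variation, for which the model has no term. Simulation assumptions: linear outcome, four equally spaced times, within-person correlation 0.3 and 0.5, 6,000 trials per setting.

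- Constant clinic effects: 4.8-5.1%.
- 20-50% of clinic variance period-specific: about 7-11% at ICC 0.01 and 13-29% at ICC 0.05.
- t-test on clinic mean slopes, 6 df: 4.7-5.7% throughout.

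**5. Detectable difference.** Solve d = (t₀.₉₇₅,₆ + t₀.₈₀,₆) × √{[p0(1−p0) + p1(1−p1)]/200 × DE}, with p1 = p0 + d and 2.447 + 0.906 = 3.353. Under independence the multiplier is 1.96 + 0.84 = 2.80. The control rate p0 = 60% and 80% power are assumed.

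| Analysis | Detectable difference |
|---|---|
| Independence | 13.1 points |
| 6 df, ICC 0 | 15.5 points |
| 6 df, ICC 0.01 | 18.5 points |
| 6 df, ICC 0.02 | 20.9 points |
| 6 df, ICC 0.05 | 26.3 points |

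The control rate matters: at ICC 0.01 the figure is 19.7 points for 50% and 11.6 for 85%.

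**The case against.** The strongest reply is that the plan does not hide the problem. It puts clinic-level t-tests first, admits the small number of clusters, and promises ICC sensitivity analyses. That is fair, and it narrows the gap: a valid test is mentioned but is not made decisive. It does not close the gap, because the paragraph that names the primary outcomes tests them only by individual-level regression, and an unspecified ICC range can be chosen after the results are known.

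Second, the 11-29% rests on an assumed ICC. This stands as a limit on the size of the problem, since at ICC 0.001 the error is only 5.6%. But the plan itself expects to vary the ICC, and nothing in it argues for a value near zero.

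Third, Primary Aim 1 can be read as making delta, not the logistic coefficient, decisive for adherence. If so, the 11-29% does not apply to that analysis. The reading taken here is that both are planned. The ambiguity is one more reason to name the deciding analysis.

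Fourth, the delta figures are indicative only. They use a linear outcome although adherence is coded as binary, equal spacing although the first visit is in pregnancy, and drift shares with no source in the documents. A within-person correlation of 0.7 would take the upper end to about 38%. What stands is the direction: about 5% without drift, and above 5% with it.

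**Conclusion.** The concern holds. As written, the plan allows superiority on the primary outcomes to be claimed from a test that ignores the unit of randomisation, and the stated justification does not support that choice. At an assumed two-sided 5% level and 50 women per clinic, the error is roughly double the nominal level at ICC 0.01 and nearly six times it at ICC 0.05 (29.1/5 = 5.8). These figures are per test, before any allowance for testing several PMTCT steps. They apply to the logistic tests; for delta, inflation depends on clinic-by-time variation, on which the documents give nothing. This needs settling before outcome data are seen, since a choice of test made afterwards would carry little weight.

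**What to change.** - **Deciding analysis.** For each primary outcome, state that the clinic-level comparison is primary and prevails if results disagree. The plan's own t-test on clinic summaries would do, with weighting by cluster size settled in advance. To keep covariate adjustment, fit the logistic regression with baseline covariates but without arm, take one mean residual per clinic, and compare 4 v 4 on 6 df.
- **Check.** Add an exact permutation test over the C(8,4) = 70 allocations; the smallest two-sided p is 2/70 = 0.029. This assumes unmatched randomisation, as no matching is described.
- **Delta.** Compare clinic mean slopes 4 v 4 on 6 df, or add a clinic-by-time random effect with small-sample degrees of freedom. A clinic random intercept alone does not address drift. Say whether delta or the single-stage comparison decides for adherence.
- **Sensitivity analysis.** List the ICC values now, for example 0.005, 0.01, 0.02 and 0.05, and label the unclustered regressions descriptive.
- **Sample size.** The adequacy sentence may mean only that the model can be fitted. Put beside it the difference detectable with clustering, over a range of control rates.

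The cost is SAP wording and a little analysis work, with no new data or participants. The downside is wider intervals and a less favourable account of what the trial can detect. At a 60% control rate, the 6 df alone move the detectable difference from 13.1 to 15.5 points, and an ICC of 0.01-0.05 takes it to 18.5-26.3.

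### Varying the outcome ICC suits the single-time arm comparisons but not δ, the arm-by-time effect the plan calls the intervention effect, whose precision depends on clinic-by-time variation

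*Combined protocol and SAP*

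**What the plan says.** Under Data analysis (Statistical Analysis), the plan first compares clinics by t-tests, weighted by cluster size where sizes differ. It then explains that "we do not have the 20+ clusters needed to reliably adjust standard errors for clustering", so most analyses are regressions on individual women. For clustering in those regressions, the investigators "will conduct sensitivity analyses using a range of plausible ICC values for the outcomes". No ICC value is given, nor any statement of how an ICC enters the calculation.

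Under Primary Aim 1, two kinds of analysis follow. One is logistic regression comparing the arms on binary adherence at each stage and on viral suppression. The other is a repeated-measures model with a woman-level random effect and an error term, but no clinic or clinic-by-time term. In that model δ "is the interaction of treatment group and time, and shows the intervention effect".

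**The concern.** The outcome ICC measures how alike women in one clinic are at a given time. It describes the extra variance in an arm difference at that time. δ is a different kind of quantity: a difference between arms in change over time. A clinic that is persistently better or worse than the others contributes nothing to change, so its effect drops out. What makes δ less precise than the individual-level model reports is clinics moving apart over time, for example through staffing or supply changes that affect one clinic and not another.

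The check offered for the individual-level models therefore does not measure the threat to δ. A reader could be told that δ is fragile when it is not, or robust when it is not, and varying the outcome ICC would not show which case applies.

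**Working it through.** **Inputs from the documents.** Eight clinics ("adherence to each step of the PMTCT care cascade at 8 ANC clinics in Uganda"), split 4 v 4 ("Four (4) clinics will implement usual care and 4 will implement usual care plus depression care"). Cluster size m = 50 ("At each site, 50 HIV+ newly pregnant women (total n=400) who screen positive for potential depression will be enrolled"). Four surveys ("survey them at baseline, month 6, 12 and 18 following delivery"). The only stated figure that can be reproduced is the total: 8 × 50 = 400. No ICC, design effect, alpha, power or effect size is given.

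**Assumed inputs.** Outcome ICC 0.05, with 0.01 as an alternative. Correlation r = 0.5 between two surveys of the same woman. CAC, the correlation of a clinic's effect between surveys, from 1 (fully stable) to 0. Clinic-by-survey effects independent across surveys, a continuous outcome, total variance 1 and full follow-up.

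**Step 1: arm difference at one time.** The variance inflation factor is 1+(m−1)ICC. At ICC 0.05 this is 1 + 49 × 0.05 = 3.45. At ICC 0.01 it is 1 + 49 × 0.01 = 1.49.

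**Step 2: δ.** Write the outcome as clinic + clinic-by-survey + woman + error. The clinic and woman terms cancel from within-woman change. What remains has variance 1−r per survey, of which ICC(1−CAC) is shared by all women in the clinic. The ICC that matters for δ is therefore ρ = ICC(1−CAC)/(1−r), and the factor is 1+(m−1)ρ. It equals the Step 1 factor only if CAC happens to equal r.

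**Step 3: results at ICC 0.05.** The last column is the standard error corrected by the outcome-ICC factor, divided by the right one.

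| CAC | ρ | Factor for δ | Outcome-ICC factor | SE ratio |
|---|---|---|---|---|
| 1 | 0.05×0/0.5 = 0 | 1.00 | 3.45 | √(3.45/1.00) = 1.86 |
| 0.8 | 0.05×0.2/0.5 = 0.02 | 1.98 | 3.45 | √(3.45/1.98) = 1.32 |
| 0.5 | 0.05×0.5/0.5 = 0.05 | 3.45 | 3.45 | 1.00 |
| 0 | 0.05×1/0.5 = 0.10 | 5.90 | 3.45 | √(3.45/5.90) = 0.76 |

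At ICC 0.01 the ratio runs from √(1.49/1.00) = 1.22 at CAC 1 to √(1.49/1.98) = 0.87 at CAC 0.

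**Step 4: simulation.** Under no effect, with the planned layout and the same assumptions at ICC 0.05, the simulated factors for δ were 1.02, 1.86, 3.51 and 5.96 at CAC 1, 0.8, 0.5 and 0, in line with the formula. A 4 v 4 t-test on clinic slopes rejected about 5% of the time throughout.

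**Step 5: other forms of drift.** The formula in Step 2 belongs to independent clinic-by-survey effects. If clinics instead follow their own linear trends, the ratio at ICC 0.05 is 0.88–1.18 with 10% of clinic variance in trends, 0.67–0.94 with 20% and 0.46–0.65 with 50% (within-clinic correlation of a woman's values 0.7 down to 0.3). Dichotomising the outcome, with 0.05 as the ICC before dichotomising, left the stable-clinic ratio at 1.83. With half the clinic variance in trends and correlation 0.5, it gave 0.82 against 0.56 for the continuous outcome.

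**Step 6: ICC used as a clinic random intercept.** In balanced data a clinic intercept, like the woman's, cancels from δ. The standard error of δ is then essentially unchanged whatever ICC is chosen. That is harmless if clinics are stable, but drift is missed entirely.

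**The case against.** Four points on the other side have weight.

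- **The plan states no formula.** A reader might infer that 3.45 is the plan's own inflation factor. It is not: no ICC value and no method of applying one is given, and 3.45 is an illustration. The criticism survives because neither natural use of an outcome ICC (Steps 2 and 6) measures drift.
- **The plan uses a range.** In the Step 3 table ρ runs from 0 to 0.10, so an assumed sensitivity range of 0 to 0.10 would cover it. That is true, but a range chosen as plausible for the outcomes does not say which value applies to δ. With half the clinic variance in linear trends and correlation 0.7, the factor of 16.6 corresponds to an effective ICC of (16.6−1)/49 = 0.32, outside that range.
- **Clustering is respected elsewhere.** A reader might infer that δ has no possible protection in the plan. The clinic-level t-tests respect clustering and need no ICC. But the plan does not say whether they compare baseline values, follow-up values or changes, so as written they cannot be counted as a check on δ. The outcome ICC is also the relevant quantity for the single-time logistic comparisons.
- **A sensitivity analysis is not a decision rule.** Reading the standard-error ratios as the trial's false-positive rate or power would go beyond the documents, which do not make this check the deciding test.

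A reader might also extend the argument to Secondary Aims 1 & 2, which "explore the relationship between change in depression and outcomes over time". The documents do not support a size there. A factor built from the product of exposure and outcome ICCs fits a fixed exposure and a single-time outcome, not change. The intervention is meant to alter depression clinic by clinic, so the exposure ICC is unknown. The plan also contemplates fixed effects for these exploratory analyses.

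**Conclusion.** The point holds for δ only. The stated clustering check on the individual-level models varies a quantity that suits the single-time arm comparisons and does not govern the precision of the arm-by-time effect.

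In the illustration the corrected standard error runs from 1.86 to 0.76 times the right one at ICC 0.05, and from 1.22 to 0.87 at ICC 0.01. At CAC 0.5 with r 0.5 the two agree, by coincidence. Both size and direction rest on the assumed ICC, CAC, r and pattern of drift, none of which the documents give. Too wide follows if clinics are stable and the ICC is used as an inflation factor; too narrow needs substantial drift. Since varying the outcome ICC cannot distinguish these cases, the mismatch should be corrected and not left to interpretation.

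**What to change.** Keep the outcome-ICC sensitivity analysis for arm comparisons at a single time, and state how the ICC is applied. For δ, do one of the following:

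- Estimate a time slope or mean change for each clinic and compare the eight values, 4 v 4, by the clinic-level t-test already planned. This has 8 − 2 = 6 degrees of freedom and needs no ICC.
- Vary the clinic-by-time variance, equivalently the ICC of change, in the sensitivity analysis for δ.

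The cost is SAP wording and a few lines of analysis code, with no new data. The downside of the first option is a wider interval: the 95% multiplier on 6 degrees of freedom is 2.447 against 1.960 for a normal approximation, a ratio of 2.447/1.960 = 1.25.
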